12.3 Reporting Procedures for Serious Adverse Events

All SAEs occurring during the trial must be reported to GW with any other supporting information and recorded in the AE section of the eCRF. Any ongoing SAEs should be followed up until resolution, wherever possible. For all deaths, the working diagnosis or cause of death as stated on a death certificate, available autopsy reports, and relevant medical reports should be sent to GW promptly.

All SAEs must be recorded in the eCRF within 24 hours of discovery or notification of the event. GW Research Ltd PVD will be automatically notified that an SAE has been recorded. Any additional information required for a case (follow-up or corrections to the original case) will be requested by GW PVD through eCRF queries.

The investigator should continue to document all AEs that occur up to the last formal safety follow-up (Visit 16). If the investigator subsequently becomes aware of any deaths or a new GWP42003-P-related SAE after the last formal follow-up period of the trial, these should still be reported to GW PVD.

Any other problem discovered after Visit 10 that is deemed to be an unexpected safety issue and is likely to have an impact on patients who have taken part in the trial must be

Study Code: GWND19002
EudraCT Number: 2019-001605-24
Clinical Protocol V2 18Dec19

treated as an SAE and reported to GW PVD. Such post-trial SAEs do not need to be recorded on the patient's eCRF if editing rights to the eCRF have been removed due to the final trial data lock. GW Research Ltd PVD may request safety follow-up information after the final trial visit in order to investigate a potential safety issue.

Contact details for GW PVD are provided at the front of the center files for all trial centers.

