12.3 Reporting Procedures for Serious Adverse Events

All SAEs occurring during the trial must be reported to GW with any other supporting information and recorded in the AE section of the eCRF. Any ongoing SAEs should be followed up until resolution, wherever possible. For all deaths, the working diagnosis or cause of death as stated on a death certificate, available autopsy reports, and relevant medical reports should be sent to GW promptly.

All SAEs must be recorded in the eCRF within 24 hours of discovery or notification of the event. GW Research Ltd PVD will be automatically notified that an SAE has been recorded. Any additional information required for a case (follow-up or corrections to the original case) will be requested by GW PVD through eCRF queries.

The investigator should continue to document all AEs that occur up to the last formal follow-up observational period (Visit 10). If the investigator subsequently becomes aware of any deaths or a new GWP42003-P-related SAE after the last formal follow-up period of the trial, these should still be reported to GW PVD.

Any other problem discovered after Visit 10 that is deemed to be an unexpected safety issue and is likely to have an impact on patients who have taken part in the trial must be

Study Code: GWND19002
EudraCT Number: 2019-001605-24
Clinical Protocol V1 09Aug19

treated as an SAE and reported to GW PVD. Such post-trial SAEs do not need to be recorded on the patient's eCRF if editing rights to the eCRF have been removed due to the final trial data lock. GW Research Ltd PVD may request safety follow-up information after the final trial visit in order to investigate a potential safety issue.

Contact details for GW PVD are provided at the front of the center files for all trial centers.

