9.1.2 Dipstick urinalysis (provided urine can be obtained)Telephone Visits

9.1.2.1 Visits 2 (Day 8 [± 3]) and 3 (Day 15 [± 3])

A visit window of ± 3 days from the scheduled visit date is permitted, but it is preferred that the visit is performed on the scheduled visit day, where possible.

Telephone visits will be conducted by a center nurse (the center investigator only needs to be involved if necessary, e.g., if any concerns are raised during the call). Information regarding changes to concomitant medications and AEs will be reviewed. The center (the nurse and, if necessary, the investigator) must assess adherence to the dosing schedule.

Study Code: GWND19002
EudraCT Number: 2019-001605-24
Clinical Protocol V2 18Dec19

9.1.2.2 Visit 16 (28 days after last dose IMP [+ 7], Follow-up, End of Trial)

A visit window of + 7 days from the scheduled visit date is permitted, but it is preferred that the visit is performed on the scheduled visit day, where possible. This visit marks the end of the trial.

Visit 16 constitutes the last scheduled safety follow-up. The purpose of the visit is to ascertain the status of AEs continuing after the cessation of GWP42003-P or any new AEs commencing after discontinuation. All causally related AEs that result in a patient's early termination from the trial or are present at the end of the trial should be followed up until a satisfactory resolution occurs, i.e., until the AE resolves or is considered clinically insignificant, or until the investigator is satisfied that the AE is not related to GWP42003-P and needs no further investigation. Information regarding changes to concomitant medications will be reviewed.

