12.2 Serious Adverse Events

During clinical investigations, AEs may occur, which if suspected to be GWP42003-P-related, might be significant enough to lead to important changes in the way GWP42003-P is developed (e.g., change in dose, population, monitoring need, consent/assent forms). This is particularly true for events that threaten life or function. Such SAEs will be reported promptly to regulatory authorities, applicable IRBs/IECs, and investigators (expedited reporting) by GW.

An AE must only be classed as serious, i.e., an SAE, when the event falls into one of the following criteria:

- Results in death
- Is life threatening^{*}

Study Code: GWND19002
EudraCT Number: 2019-001605-24
Clinical Protocol V2 18Dec19

- Requires inpatient hospitalization or prolongation of existing hospitalization
- Results in persistent or significant disability/incapacity
- Is a congenital anomaly/birth defect
- Is medically significant**

* The term “life threatening” in the definition of “serious” refers to an event in which the patient was at risk of death at the time of the event; it does not refer to an event that, hypothetically, might have caused death if it were more severe.

** Medical and scientific judgment should be exercised in deciding whether SAE reporting is appropriate in other situations. Important medical events may not be immediately life threatening or result in death or hospitalization but may jeopardize the patient or may require intervention to prevent one of the other outcomes listed in the definition above. These should also usually be considered serious. Examples of such events are intensive treatment in an emergency room or at home for allergic bronchospasm, blood dyscrasias or convulsions that do not result in hospitalization, or development of drug dependency or use of drugs of abuse.

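### Protocol V2 Section 12.3 still uses V1's end-of-trial visit number (Visit 10, now Day 365), so its post-trial SAE rule, read literally, runs during treatment and conflicts with Section 12.2

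*Protocol*

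**What the plan says.** Protocol V2, Section 12.3, sets a reporting rule whose subject is "Any other problem discovered after Visit 10 that is deemed to be an unexpected safety" matter. Where two conditions hold together, such a problem has to be "treated as an SAE and reported to GW PVD": it is an unexpected safety issue, and it is likely to affect participants. The next sentence gives an exemption from data entry and begins "Such post-trial SAEs do not need to be recorded on the"; the exemption applies only where eCRF editing rights have gone because of final data lock.

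The paragraph just above, in the same section of V2, reads "The investigator should continue to document all AEs that occur up to the last formal safety follow-up (Visit 16"). Its V1 counterpart reads "The investigator should continue to document all AEs that occur up to the last formal follow-up observational period (Visit 10"). V2 therefore updated that paragraph but not the one below it.

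V2 Section 9.1.2.2 states that "Visit 16 constitutes the last scheduled safety follow-up". V2 Section 12.2 states: "An AE must only be classed as serious, i.e., an SAE, when the event falls into one of the" listed criteria. One of those criteria is medical significance, which rests on judgment.

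**The concern.** Sections 12.2 and 12.3 are both mandatory. Section 12.2 allows the SAE label only where a listed criterion is met. Section 12.3 requires SAE handling for a qualifying problem whether or not one is met. While Visit 10 was the end of the trial, the two rules applied to different periods. With Visit 10 in the middle of treatment they overlap, and a site has two instructions for the same event.

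Safety is the primary endpoint. Serious TEAEs and treatment-related serious TEAEs are required summaries (Protocol V2 Section 13.6.2.2; SAP Section 9.1). An event classified as serious mid-trial would be entered in the eCRF, because the data-lock exemption would not yet apply, and would be counted in those tables. V2 Section 14 provides no safety monitoring committee and SAP Section 4.2.2 plans no data review meeting, so no step dedicated to this would pick up inconsistent classification.

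**Working it through.** No sample size, power or error rate is involved, and the plan gives no figure of its own to reproduce. The check compares the two protocol versions and counts days on the visit schedules.

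**Inputs** (V1 Sections 9.1.1 and 9.1.2 and Appendix 1; V2 Sections 9.1.1 and 9.1.2 and Appendix 1; SAP Table 3)

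| Milestone | Protocol V1 | Protocol V2 |
|---|---|---|
| End of treatment | Visit 8, Day 197 | Visit 14, Day 729 |
| End of taper | Visit 9, Day 207 | Visit 15, Day 739 |
| Last safety follow-up | Visit 10, Day 235 | Visit 16, Day 767 |
| Visit 10 | Day 235 (end of trial) | Day 365 (on treatment) |
| Visit named in the Section 12.3 catch-all | Visit 10 | Visit 10 |

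**Step 1: the follow-up visit is the same milestone in both versions.** Last follow-up = end of taper + 28 days. V1: 207 + 28 = 235, which is Visit 10. V2: 739 + 28 = 767, which is Visit 16. The V2 equivalent of V1's Visit 10 is therefore Visit 16.

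**Step 2: the other V2 references were moved.** V2 Sections 9.2.15, 12.1.1, 12.6 and 12.7, and the preceding paragraph of 12.3, all use Visit 16 as the end point for AE recording or follow-up. The catch-all sentence does not. This is current text: SAP Section 1 names Protocol V2 as the protocol it analyses.

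**Step 3: position of Visit 10 in V2.** Share of planned treatment elapsed = (365 − 1) / (729 − 1) = 364 / 728 = 50%.

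**Step 4: overlap with the trial under the literal reading.**
- Treatment: 729 − 365 = 364 days
- Taper: 739 − 729 = 10 days
- Follow-up: 767 − 739 = 28 days
- Total: 364 + 10 + 28 = 402 days, of 767 − 1 = 766 days from Day 1 to Visit 16 (402 / 766 = 52%)

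**Step 5: after correction.** With Visit 16 in the sentence, the rule starts after Day 767 and the overlap is zero.

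These are nominal schedule days and ignore visit windows. They measure how long the two rules overlap on paper, not how many events are affected.

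**The case against.** The strongest reply is that the context already settles the meaning. The preceding paragraph deals with AEs up to Visit 16 and then with deaths and related SAEs learned of later; the disputed sentence goes on to any other problem, refers to participation in the past tense, and is followed by a sentence that labels the events post-trial and provides for data lock. An attentive site would see the slip. This stands, and it is why the point is minor. It also shows that the right visit number is not a matter of opinion.

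A second reply is that the conflict with Section 12.2 is narrow. An unexpected issue likely to affect participants would often count as medically significant and so be serious anyway. This also stands in part: the conflict is confined to events that satisfy both Section 12.3 conditions but no Section 12.2 criterion. V1 already had the same tension for post-trial problems; the stale number brings it into the treatment period.

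A reader might go further and infer three things that the documents do not support:

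- *That every unexpected safety issue after Day 365 becomes an SAE.* The second condition, likely effect on participants, rules this out.
- *That second-year SAE counts are distorted.* The documents give no counts or rates. SAP Section 9.1 specifies no serious-event table by year; its onset-period table, which has a category beyond one year, covers all TEAEs. SAP Section 6.1.7 does not take site into account, so no planned output contrasts sites.
- *That expedited reporting follows the wrong trigger.* The sentence sends reports to the sponsor's pharmacovigilance department. Onward reporting is covered by Sections 12.2 and 12.9, which concern SAEs suspected to be drug-related, relevant SAEs and SUSARs. Any error is towards over-reporting to the sponsor.

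**Conclusion.** The cross-reference is wrong as written, in an operative reporting rule of the current protocol. Read literally, it applies for 402 planned days inside the trial and conflicts there with Section 12.2. Severity is minor.

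The supportable consequence is possible over-classification: if a site applies the sentence literally to an event that meets no Section 12.2 criterion, that event could be added to the overall serious-TEAE tables and to SAE reports to the sponsor. Its frequency cannot be estimated from the documents.

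The 50% and 52% shares are planned calendar time and should not be read as an effect size. SAP Section 1 says the extension is stopped prematurely, while SAP Section 9.5 says patients who enter will complete it under the protocol and annex. Actual exposure after Day 365 is not stated and may be well below plan. Confidence is high for the stale number and low for any effect on results.

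**What to change.** In Protocol V2 Section 12.3, replace Visit 10 with Visit 16 in the catch-all sentence. The rule then covers only discoveries after the trial, and Section 12.2 alone defines seriousness while the trial runs. Send sites a short clarification.

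For data already collected, use the clinical data management review that Protocol V2 Section 16.3 provides, since the SAP plans no data review meeting. Query any SAE reported after a patient's Visit 10 that meets no Section 12.2 criterion. Select by report or discovery date and not by onset, because the sentence turns on when a problem is discovered.

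The cost is one visit number, one letter to sites and a limited set of data queries. No analysis changes.

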12.4 Pregnancy

Any patient, or patient's partner, who has become pregnant while receiving GWP42003-P or within 90 days of the last dose of GWP42003-P must be reported to GW PVD. Where possible, the investigator should provide the outcome of the pregnancy.

All pregnancies must be recorded in the eCRF within 24 hours of awareness. GW PVD will be automatically notified that a pregnancy has been recorded. Any additional information required for a case (follow-up or corrections to the original case) will be requested by GW PVD through eCRF queries.

The investigator is not obliged to actively monitor for any pregnancies that commence more than 90 days after the final dose of GWP42003-P. However, if the investigator becomes aware of a new pregnancy outside this time limit, then he/she should report it as above. GW PVD will follow up for all pregnancy outcomes.

12.5 Causality Assessment

Causality assessment is required for all AEs and SAEs. Causality assessment must only be assigned by the investigator. All cases judged as having a reasonable suspected causal relationship to GWP42003-P must be reported as such. The expression "*reasonable causal relationship*" is meant to convey in general that there are facts (evidence) or arguments to suggest a causal relationship.

The following question, which must be answered by the investigator for all AEs, is used to capture the reasonable causal relationship of an event to GWP42003-P:

"In your opinion, is there a plausible relationship to the IMP?" The answer is either "yes" or "no."

Events that start before the first dose of the IMP (pretreatment) should be considered as not causally related. Where a pretreatment event worsens in severity following the first dose of the IMP, a new event record should be entered into the eCRF.

Study Code: GWND19002
EudraCT Number: 2019-001605-24
Clinical Protocol V2 18Dec19

Considering the explanation given above, investigators are strongly encouraged to express their opinion on what the cause of an AE might be. For individual patients, the investigator is usually in the best position to assess the underlying suspected cause of an AE. For all AEs, especially SAEs, it is important that the investigator assess not only the possible role of GWP42003-P but also other potential contributing factors. Factors for consideration of the underlying cause may include the following:

- Medical and disease history
- Lack of efficacy/worsening of treated condition
- Concomitant or previous treatment
- IMP discontinuation
- Protocol-related procedure

12.6 Reporting Procedures for All Adverse Events

All AEs (including SAEs) occurring during the trial will be reported on the running logs in the AE section of the eCRF. This includes all events from the time following screening (Visit 1) up to and including the post-trial safety follow-up visit (Visit 16), whether or not attributed to GWP42003-P and observed by the investigator or patient.

For the patient's expected seizure types, these do not routinely require documentation as AEs. However, any worsening, including a change in the pattern or severity of seizures, should be documented in the CRF if deemed to meet the definition of an AE, in the investigator's opinion.

Any AE that meets the SAE criteria should still be reported as an SAE.

The following information will need to be provided for all AEs:

A) Adverse Event (Diagnosis or Syndrome, if Known, or Signs and Symptoms)

Where the investigator cannot determine a diagnosis, signs or symptoms should be recorded in the AE section of the eCRF. Once a diagnosis has been determined, the AE section of the eCRF must be updated to reflect the diagnosis in replacement of the original symptoms. In circumstances where only a provisional diagnosis is possible (working diagnosis), the eCRF must be updated to reflect the provisional diagnosis in replacement of the original symptoms. In some circumstances, it may be relevant for the investigator to include the symptoms alongside the diagnosis in the verbatim event

Study Code: GWND19002
EudraCT Number: 2019-001605-24
Clinical Protocol V2 18Dec19

description. However, the diagnosis (full or provisional) should be clearly stated, e.g., fever and malaise due to respiratory tract infection.

B) Adverse Event Start Date and Stop Date

The start and stop dates of the event must be provided. All AEs require these fields to be completed in full. Partial dates or missing dates are not normally acceptable, and significant effort must be undertaken to obtain any unknown information. If a precise date is not known, an estimated date should be provided instead. When a complete date cannot be given, record as much information as possible (i.e., the month and year or, in exceptional circumstances, just the year). When the actual start date becomes known, the eCRF must be updated to replace the previously recorded date.

C) Outcome

The outcome of the event must be recorded accurately and classified into one of the following categories:

- Recovered
- Recovered with sequelae
- Continuing
- Patient died

D) Severity

When describing the severity of an AE, the terms mild, moderate, or severe should be used. Clinical judgment should be used when determining which severity applies to any AE.

If the severity of an AE fluctuates day to day, e.g., a headache or constipation, the change in severity should not be recorded each time; instead, only the worst observed severity should be recorded, with the AE start and stop dates relating to the overall event duration, regardless of severity.

A severe AE is not the same as an SAE. For example, a patient may have severe vomiting, but the event does not result in any of the SAE criteria above. Therefore, it should not be classified as serious.

E) Causality

See [Section 12.5](#).

Study Code: GWND19002
EudraCT Number: 2019-001605-24
Clinical Protocol V2 18Dec19

F) Action Taken with IMP

This question refers to the action taken with GWP42003-P due to an AE. The action with GWP42003-P must be classified as follows:

- None
- Dose reduced temporarily
- Dose reduced
- IMP interrupted
- IMP stopped

12.7 Follow-up Procedures for Adverse Events

The investigator may be asked to provide follow-up information to GW PVD for any AEs reported or during the investigation of potential safety issues. Such requests for additional safety information may occur post follow-up Visit 16, after the trial.

Adverse events considered related to GWP42003-P by the investigator or the sponsor should be followed up until resolution or the event is considered stable.

It will be left to the investigator's clinical judgment whether or not an AE is of sufficient severity to require the patient's removal from treatment. A patient may also voluntarily discontinue from treatment due to what he/she perceives as an intolerable AE. Further details of discontinuation are presented in [Section 10](#). If either of these occurs, the patient must permanently discontinue from treatment and be given appropriate care under medical supervision until symptoms cease or the condition becomes stable. If a safety concern is identified following withdrawal of a patient, GW may contact the investigator for additional follow-up information.

12.8 Potential Cases of Drug-induced Liver Injury

All investigational centers are required to submit to GW PVD the laboratory results for any patient after randomization who meets the criteria for the selected laboratory parameters as follows:

- ALT or AST $> 3 \times$ ULN with the appearance of fatigue, nausea, vomiting, right upper quadrant pain or tenderness, fever, rash, and/or eosinophilia ($> 5\%$)
- ALT or AST $> 8 \times$ ULN

Study Code: GWND19002
EudraCT Number: 2019-001605-24
Clinical Protocol V2 18Dec19

- ALT or AST > 5 × ULN for more than 2 weeks
- ALT or AST > 3 × ULN **and** (TBL > 2 × ULN **or** INR > 1.5)

These reports must be sent to GW PVD via e-mail (see [Appendix 2.2](#)) within 24 hours of becoming aware of the results. In addition, a copy of the patient's baseline laboratory results with all reports should be sent to GW PVD.

Abnormal values in AST and/or ALT concurrent with abnormal elevations in TBL that meet the criteria outlined above are considered potential cases of drug-induced liver injury and will be considered as protocol-defined criteria for treatment discontinuation and important medical events. The investigator will arrange for the patient to return to the investigational center as soon as possible (within 24 to 48 hours of notice of abnormal results) for a repeat assessment of ALT, AST, TBL, alkaline phosphatase, gamma-glutamyl transferase levels, eosinophils as well as for testing INR (prothrombin time), detailed history; and physical examination. Patients should be followed this way until all abnormalities have normalized (in the investigator's opinion) or returned to the baseline state. However, if the above transaminase elevation criteria are confirmed by the first set of follow-up laboratory tests, the patient must be withdrawn from the trial.

Elevations in ALT or AST > 3 × ULN **or** TBL > 2 × ULN alone are not considered potential cases of drug-induced liver injury but will be followed as detailed above, within 72 hours' notice of abnormal results. In cases where after Visit 1, ALT or AST are > 3 × ULN, INR testing must be requested. If only the hepatic function monitoring panel was requested and ALT or AST > 3 × ULN, both INR and hematology panel (eosinophils) must be requested. If the patient cannot return to the investigational center, repeat assessments may be done at a local laboratory, and the results should be sent to GW PVD.

